**Study Summary**

Title	Efficacy of a Novel Collagenase Clostridium Histolyticum Protocol for Peyronie's Disease Among Prior Non-responders: A Randomized, Controlled, Single-blinded Study
IRB Protocol Number	20213914
Methodology	Prospective, randomized, controlled, single-blinded
Overall Study Duration	2 years
Subject Participation Duration	1 year
Objectives	Compare key clinical outcomes between controls and men treated with a novel CCH protocol among men previously unresponsive to CCH administration.
Number of Subjects	40
Diagnosis and Main Inclusion Criteria	Men >18 years of age with Peyronie's Disease, current curvature of 30 degrees or more, prior treatment with 6-8 injections of CCH, and prior minimal (<20% and/or <10 degrees) responsiveness to CCH administration.
Randomization	Patients will be randomized 1:3 to control (no treatment) or CCH (up to 8 injections). Patients in the control arm will subsequently be crossed over to CCH treatment after 6 months. Randomization tables will be created and pre-stratified based on baseline penile curvature.
Follow-up Period and Assessments	Men will have objective assessments of curvature and length and standardized and non-standardized questionnaires obtained at various time points (baseline, 6-weeks following completion of CCH, and at the end of the no treatment phase).
Statistical Methodology	Stratification of subjects prior to randomization to assure an equal representation based on baseline penile curvature (30-44, 45-59, 60-74, 75-89, 90 or above). Statistical comparisons between groups and to baseline will be made of responses to subjective questionnaires and objective measures.
Plan for Publication	It is anticipated that the primary study will be published following accumulation of data out to 1 year. Pending novelty of findings, additional studies may also be published if felt to be warranted (subset analyses).

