### 1.2 Investigational Treatments

The current study would randomize men 1:3 into one of two treatment cohorts: 1. Observation followed by CCH or 2. CCH followed by observation. This study design offers the benefits of a randomized,

controlled trial (highest level of evidence), while also providing data for a second set of publications evaluating the cross-over to treatment phase (for controls). RCTs are particularly important in PD, where the disease changes over time in a percentage of men as a function of its natural history. This would also allow blinding of measurements using photographs (single-blinded assessments), which provides further study rigor. See Figure 1 for overall study schema.

1. No treatment (control) followed by CCH. Men in this cohort would undergo baseline assessments followed by no treatment for 6 months and then repeat assessments. Men would then cross-over to CCH treatment and undergo up to 8 injections (or until curvature is <15 degrees). Interval assessments would be performed with the 1st injection of each series, and final assessments would then be performed 6 weeks following the final injection.
2. CCH followed by no treatment. Men in this cohort would undergo baseline assessments followed by up to 8 injections of CCH (or until curvature is <15 degrees). Interval assessments would be performed with the 1st injection of each series and 6 weeks following completion of treatment. Men then would not undergo any additional treatments for 6 months, after which final assessments would then be performed.

During CCH administration, several key differences from the IMPRESS protocols would be performed. Please note that each of these changes have been slowly implemented in the investigators' practice over time to improve overall efficacy of therapy:

	IMPRESS Protocol	Current Study Protocol
Amount administered	0.58 mg	0.9 mg
Suspension volume	0.37 ml	0.7 ml
Method of injection	Into plaque	To point of maximal curvature in the tunica, as determined with an erection at the first injection of each series
Administration schedule	1-3 days apart	1 day apart
Mechanical device traction	None	RestoreX 30-60 min daily until 6 weeks after final injection
Office modeling	Performed 1-3 days after initial injections (defined as "firm")	10-15 lbs of force performed at the time of 2 nd injection

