## **2 Study Endpoints**

### **2.1 Primary Endpoints**

1. Compare penile curvature between control and treatment groups at 6 months
2. Compare PDQ outcomes between control and treatment groups at 6 months

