### **2.2 Secondary Outcomes**

1. Compare IIEF outcomes between control and treatment groups at 6 months
2. Compare penile curvature changes in control men at baseline and 12 months (i.e. prior to and following cross-over to CCH)
3. Compare penile length changes in control men at baseline and 12 months (i.e. prior to and following cross-over to CCH)
4. Compare PDQ changes in control men at baseline and 12 months (i.e. prior to and following cross-over to CCH)
5. Compare IIEF changes in control men at baseline and 12 months (i.e. prior to and following cross-over to CCH)
6. Compare penile length changes between control and treatment groups at 6 months
7. Report adverse events at 6 and 12-month time points

8. Report changes in penile curvature between 6 and 12-month assessments for CCH men

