### 3.4 Consent and Enrollment

Patients attending the Male Fertility and Peyronie’s Clinic or noting interest via email will receive a description of the study. Those interested in participating, will be given the opportunity to meet with the study coordinator to further review study details and formal consent.

Patients that would like additional time to consider their participation will be given another opportunity to meet with the study coordinator at a later time. If the patient expresses interest in participating at any time, a formal consent will be reviewed.

At enrollment, all participants will be assigned a study identifier, with a master list maintained in a password protected database linking the patient to the identifier. A total of up to 40 patients will be enrolled to achieve outcomes of at least 30 men (total study power 40 given that each participant will serve as a control as well as treatment comparator).

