### **5.2 Statistical Analysis**

The current study is considered exploratory in nature. Analyses will be performed using comparisons within and between patient cohorts. All captured data will be utilized as a point of comparison based on accepted standards (e.g. IIEF subdomains, PDQ subdomains, etc.). All data will be analyzed to determine if it is normative / non-normative and will be described and compared appropriately (mean, SD versus median, IQR).

Patients with partial missing data will have all available data included for analysis, with no attempts made to statistically replace missing variables. All data will be analyzed using an intent-to-treat analysis.

Adverse events will be reported as a total as well as compared between cohorts.

A power analysis was performed using historical data from another one of the investigators' RCTs to determine the standard deviation for control men between two sequential assessments. Results of absolute curvature improvements demonstrated a standard deviation of 16 degrees or 27% relative improvement. Using a 0.05 alpha threshold, power of 80%, and expected cohort size of 30 (assuming 30 with 6-month data) this would allow us to distinguish differences over 17 degrees or 29%. Given the investigators' current improvements of 60% with the investigators' preliminary data, we would expect this study to have sufficient power to demonstrate a clinically and statistically significant finding.

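### The 17-degree (29%) detectable difference in section 5.2 does not follow from 30 evaluable men randomised 1:3; two-sided, it is about 19 to 20 degrees (32 to 34%)

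*Combined protocol and SAP*

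**What the plan says.** Section 5.2 (Statistical Analysis) describes the study as exploratory and then gives a power statement. The variability comes from an earlier trial by the same investigators, used "to determine the standard deviation for control men between two sequential assessments": 16 degrees, or 27% in relative terms. With alpha 0.05 and 80% power, the section continues: "expected cohort size of 30 (assuming 30 with 6-month data) this would allow us to distinguish differences over 17 degrees or 29" per cent. The test, its sidedness and the number of men per arm are not given.

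The Study Summary fixes the allocation: "Patients will be randomized 1:3 to control (no treatment) or CCH (up to 8 injections"). Section 1.2 repeats the 1:3 ratio. The first primary endpoint in section 2.1 is a between-arm comparison without a stated direction: "Compare penile curvature between control and treatment groups at 6 months".

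Section 3.4 presents 30 as the evaluable total: "A total of up to 40 patients will be enrolled to achieve outcomes of at least 30 men". It then adds in parentheses: "total study power 40 given that each participant will serve as a control as well as treatment comparator".

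**The concern.** For a fixed total, a two-arm comparison is most precise with equal arms. At 1:3 the control arm is only a quarter of the sample, so the detectable difference should be visibly larger than at 1:1. The stated pair is what equal arms give, which suggests that the allocation ratio was left out.

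The figure matters because a reader will use it to interpret a null or modest result. If 17 degrees carries 80% power, a true difference of that size is missed one time in five; if power is really about 68%, it is missed nearly one time in three.

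The clause in section 3.4 raises a related doubt. It suggests that the effective sample is larger than the number randomised because everyone contributes to both sides of the comparison.

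**Working it through.** **Inputs.** SD 16 degrees or 27%, alpha 0.05, power 80%, 30 men with 6-month data (section 5.2); allocation 1:3 (Study Summary, section 1.2).

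**Assumptions, because the plan is silent.** A two-sample t-test; the control-arm SD applies equally to the CCH arm; losses are proportional in the two arms, so that 30 men split 7.5:22.5, in practice 8:22 or 7:23.

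**Formula.** Detectable difference = δ × SD × √(1/n₁ + 1/n₂), where δ is the noncentrality at which the t-test with n₁ + n₂ − 2 degrees of freedom has 80% power. With 28 degrees of freedom, the two-sided 0.05 critical value is 2.048 and δ = 2.902. One-sided, they are 1.701 and 2.549.

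**Step 1: reproduce the plan's figure.** At 15:15, √(1/15 + 1/15) = 0.3651.
- Degrees: 2.902 × 16 × 0.3651 = 16.96
- Relative: 2.902 × 27 × 0.3651 = 28.6%

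These round to 17 and 29%.

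**Step 2: put in the planned allocation.** At 7.5:22.5, √(1/7.5 + 1/22.5) = 0.4216.
- Degrees: 2.902 × 16 × 0.4216 = 19.6
- Relative: 2.902 × 27 × 0.4216 = 33.0%

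**Step 3: power at the stated difference.** At 7.5:22.5 the noncentrality for 17 degrees is 17 / (16 × 0.4216) = 2.52, which gives power 0.682.

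| Evaluable split, test | Detectable difference at 80% power | Power at 17 degrees | Power at 29% |
|---|---|---|---|
| 15:15, two-sided | 16.96 degrees / 28.6% | 80% | 81% |
| 7.5:22.5, two-sided | 19.6 / 33.0% | 68% | 69% |
| 8:22, two-sided | 19.2 / 32.4% | 70% | 71% |
| 7:23, two-sided | 20.0 / 33.8% | 66% | 67% |
| 7.5:22.5, one-sided | 17.2 / 29.0% | 79% | 80% |
| 9.5:28.5 (38 men), two-sided | 17.3 / 29.1% | 79% | 80% |
| 10:30 (40 men), two-sided | 16.8 / 28.3% | 81% | 82% |

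**Step 4: the anticipated effect.** Section 5.2 relies on a 60% improvement in preliminary data. With SD 27%, two-sided, 7.5:22.5, power is 92% for a 40-point difference between arms, 97% for 45, 99% for 50 and above 99% for 60. The 40 and 45 points assume that controls change by 20 or 15 points; the plan gives no figure for control change.

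**Step 5: the clause in section 3.4.** Under sections 1.2 and 3.5, men allocated to CCH first go from baseline straight to injections. Their no-treatment phase comes only afterwards: "Men then would not undergo any additional treatments for 6 months, after which final assessments would then be performed". That is follow-up after treatment, not an untreated control period. Section 2.2 restricts the before-and-after cross-over comparisons to the control arm, for example: "Compare penile curvature changes in control men at baseline and 12 months (i.e. prior to and following cross-over to CCH"). At 1:3, only 40 × 1/4 = 10 of the men enrolled, or 7 to 8 of 30 evaluable, have both an untreated and a treated period. This clause does not enter the 17-degree calculation.

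**The case against.** The strongest reply is that no arithmetic slip is proved. With 30 men at 1:3, a one-sided 0.05 test gives 17.2 degrees and 29.0%, which also rounds to the stated pair and is closer on the percentage than equal arms. This stands as far as it goes: the documents do not show how the figure was obtained. But nothing in the plan declares a one-sided test, and the primary endpoints are worded without direction.

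A second reply is that the protocol often uses the word cohort for an arm, so 30 could be the CCH arm of 40 men. At 10:30, two-sided, the stated claim is met. Section 3.4, however, gives 30 as the evaluable total from up to 40 enrolled, and this reading would need every enrolled man to be evaluable.

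Third, 30 is a floor and losses need not be proportional. If they fell mainly on the CCH arm, 10:20 would give 18.0 degrees and 30.3%, with 75% power at 17 degrees. The shortfall is smaller but remains.

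Fourth, the study is labelled exploratory, 17 degrees is an output rather than the effect expected, and men treated first do have an assessed period off treatment. All true. These points limit the consequence; they do not make the figure or the clause correct.

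**Conclusion.** The concern holds. Under a two-sided 0.05 t-test with a common SD, 30 evaluable men at 1:3 can detect about 19.6 degrees or 33.0% with 80% power (19.2 to 20.0 degrees and 32.4 to 33.8% over the whole-number splits), not 17 degrees or 29%. The chance of missing a true 17-degree difference is about 32%, not 20%. This rests on two-sided testing, on losses in proportion to allocation, and on an SD from control men carrying over to treated men, which the plan does not state.

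The error is confined to the stated sensitivity. The conclusion of sufficient power for an effect near 60% stands. The clause in section 3.4 is contradicted by sections 1.2, 2.2 and 3.5 whatever the sidedness. Both points should be corrected; neither undermines the design.

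**What to change.** In section 5.2, name the test, the sidedness and the expected evaluable number in each arm, and restate the figure. Suggested wording:

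> With a two-sided 0.05 two-sample t-test, a common SD of 16 degrees (27%) taken from control men, and 30 evaluable men split 1:3 (about 7 to 8 control and 22 to 23 CCH), the study has 80% power to detect about 19.6 degrees or 33%. Power for a 17-degree difference is about 68%.

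A sentence on the anticipated effect may be added (for example, about 97% power for a 45-point difference), provided that the assumed control change behind it is stated. If one-sided testing was intended, say so explicitly; 17 degrees and 29% can then stay.

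In section 3.4, delete the parenthetical clause on study power and state that only men randomised to control first contribute both an untreated and a treated period.

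The cost is a few sentences of protocol text and a slightly less favourable figure. No extra patients are needed, and neither design nor analysis changes.

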## 6 Safety and Adverse Events

### Definition of Adverse Event

Unanticipated Problems Involving Risk to Subjects or Others (UPIRTSO) - any unanticipated problem or adverse event that meets the following three criteria:

Serious: Serious problems or events that results in significant harm, (which may be physical, psychological, financial, social, economic, or legal) or increased risk for the subject or others (including individuals who are not research subjects). These include: (1) death; (2) life threatening adverse experience; (3) hospitalization - inpatient, new, or prolonged; (4) disability/incapacity - persistent or significant; (5) breach of confidentiality and (6) other problems, events, or new information (i.e. publications, interim findings, product labeling change) that in the opinion of the local investigator may adversely affect the rights, safety, or welfare of the subjects or others, or substantially compromise the research data, AND

Unanticipated: (i.e. unexpected) problems or events are those that are not already described as potential risks in the protocol, consent document, or not part of an underlying disease. A problem or event is "unanticipated" when it was unforeseeable at the time of its occurrence. A problem or event is "unanticipated" when it occurs at an increased frequency or at an increased severity than expected, AND

Related: A problem or event is "related" if it is possibly related to the research procedures.

Adverse Event - an untoward or undesirable experience associated with the use of a medical product (i.e. drug, device, biologic) in a patient or research subject.

Serious Adverse Event - adverse events are classified as serious or non-serious. Serious problems/events can be well defined and include:

- Death
- Life threatening adverse experience
- Hospitalization
- Inpatient, new, or prolonged; disability/incapacity
- And/or per protocol may be problems/events that in the opinion of the sponsor-investigator may have adversely affected the rights, safety, or welfare of the subjects or others, or substantially compromised the research data.

All AEs that do not meet any of the criteria for serious, should be regarded as non-serious AEs.

### 6.1 Adverse Event Reporting Period

For the current study, the treatment follow-up period is defined as 6 weeks following the last administration of study treatment (for new symptoms).

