## **6.2 Preexisting Condition**

A preexisting condition is one that is present at the start of the study. A preexisting condition should be recorded as an adverse event if the frequency, intensity, or the character of the condition worsens during the study period.

At screening, any clinically significant abnormality should be recorded as a preexisting condition. At the end of the study, any new clinically significant findings/abnormalities that meet the definition of an adverse event must also be recorded and documented as an adverse event.

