## **6.3 Post-study Adverse Event**

All unresolved AEs will be followed by the study team until the events are resolved, the subject is lost to follow-up, or the AE is otherwise explained. A review of AEs which the subject or subject's physician believe might reasonably be related to participation in the study will be performed up to 12 months following treatment.

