## **6.5 Recording of Adverse Events**

The study team will seek information on adverse events by specific questioning between baseline and the follow-up visits. Information on all adverse events will be recorded immediately in the adverse event section of the specific questionnaire as well as in an adverse event form.

All adverse events occurring during the study period will be recorded. The clinical course will be followed until resolution, stabilization, or until it has been ultimately determined that the study treatment or participation is not the probable cause. Serious adverse events that are still ongoing at the end of the study period will be followed up, to determine the final outcome. Any serious adverse event that occurs after the study period and is considered to be at least possibly related to the study treatment or study participation will be recorded and reported immediately.

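### Section 6.1's 6-week limit for new symptoms conflicts with recording throughout the study and reporting at 12 months, and section 5.2 compares adverse events between cohorts without stating a period

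*Combined protocol and SAP*

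**What the plan says.** Five places in the combined protocol and SAP bear on which adverse events are recorded and when:

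- Section 6.1 (Adverse Event Reporting Period): "the treatment follow-up period is defined as 6 weeks following the last administration of study treatment (for new symptoms".
- Section 6.5 (Recording of Adverse Events): "All adverse events occurring during the study period will be recorded". The method is stated as: "The study team will seek information on adverse events by specific questioning between baseline and the follow-up visits". The end of the study period is not defined there.
- Section 2.2, item 7: "Report adverse events at 6 and 12-month time points".
- Section 6.3 (Post-study Adverse Event): unresolved events are followed up, and a review of events that the subject or his physician thinks reasonably related to participation "will be performed up to 12 months following treatment".
- Section 6.2 (Preexisting Condition): "At the end of the study, any new clinically significant findings/abnormalities that meet the definition of an adverse event must also be recorded".

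The analysis rule is one sentence in section 5.2: "Adverse events will be reported as a total as well as compared between cohorts". It gives no time window and no exposure basis. Under section 3.5, the CCH-first arm has about 6 months without treatment after its 6-week assessment. Controls have 6 months without treatment, then CCH, then a final assessment 6 weeks after the last injection.

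**The concern.** Section 6.1 carries the title of the reporting period and sets a limit for new symptoms. In the CCH-first arm that limit, counted from the last injection, falls at the 6-week visit, exactly where the no-treatment phase begins. Staff who learn of a new, non-serious symptom 3 months later find it outside the window in 6.1 and to be recorded under 6.5. Different staff could resolve this differently, and the 12-month safety report would then depend on which section was followed.

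The second issue is the open-ended cohort comparison in 5.2. Before crossover, the cohorts are randomised CCH and no treatment. By 12 months both are due to have had CCH. If events are accumulated over the whole study and compared by cohort, a similar rate in the two arms would say little about whether CCH causes events, yet it could be read as reassurance.

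**Working it through.** The plan gives no figure to reproduce on this point. The check is a timeline and a side-by-side reading of the rules.

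**Inputs**
- Allocation is 1:3 control to CCH, with up to 40 men and outcomes wanted on at least 30 (Study Summary; section 3.4).
- Up to 8 injections, 1 day apart within a series (section 1.2). I assume 4 series of 2.
- The interval g between series is not stated. I tried 4, 6 and 8 weeks.
- CCH-first arm: assessment 6 weeks after treatment, then 6 months (26 weeks) untreated, then final assessment (section 3.5).
- Daily traction runs until 6 weeks after the final injection (table in section 1.2). Section 6.1 does not say whether this counts as study treatment.

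**CCH-first arm, weeks from start of treatment** (the 1-day offset is ignored)
- Last injection: L = 3g
- Window end counted from the last injection: W = L + 6
- Window end if traction counts: W2 = (L + 6) + 6 = L + 12
- Final assessment: F = L + 6 + 26 = L + 32
- Gap: F − W = 26 weeks, or F − W2 = 20 weeks, whatever g is

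| g | L | W | F | Gap from injection (share of F) | W2 | Gap if traction counts (share of F) |
|---|---|---|---|---|---|---|
| 4 | 12 | 18 | 44 | 26 (59%) | 24 | 20 (45%) |
| 6 | 18 | 24 | 50 | 26 (52%) | 30 | 20 (40%) |
| 8 | 24 | 30 | 56 | 26 (46%) | 36 | 20 (36%) |

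A man who stops injections early has a smaller L, but the gap is the same.

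**Men affected.** 40 × 3/4 = 30 at full enrolment; 30 × 3/4 = 22.5, so 22 or 23, if only 30 men are followed.

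**Control arm.** The last crossover injection is at week 26 + L = 38, 44 or 50. Adding 6 gives 44, 50 or 56, which is the final assessment. So there is no gap after crossover. The untreated first 26 weeks fall before that end point.

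**How each rule treats a new, non-serious event in the CCH-first arm's untreated phase**
- 6.1: outside the window for new symptoms.
- 6.5: recorded, if the study period runs to the final visit.
- 2.2 item 7: belongs in the 12-month report.
- 6.3: reviewed up to L + 52 = week 64, 70 or 76, past the final assessment, but only if someone believes it related.
- 6.2: recorded if it is a new, clinically significant finding at the end of the study.

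The last four point towards capture, two of them conditionally. Section 6.1 points the other way.

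**Cohort comparison.** At the final assessment, time since the last injection is 6 + 26 = 32 weeks in the CCH-first arm and 6 weeks in controls. Both arms are by then due to have had CCH. A cumulative comparison is therefore immediate against delayed CCH with unequal time after treatment. Up to crossover, it is CCH against no treatment.

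**The case against.** The strongest reply is that these sections do different jobs. Section 6.1 defines a treatment follow-up period, and nothing in it says that collection stops. Section 6.5 requires recording throughout the study with active questioning, and extends to "Any serious adverse event that occurs after the study period and is considered to be at least possibly related to the study treatment". Sections 6.2 and 6.3 add end-of-study findings and a later review. Item 7 in section 2.2 reports events and does not compare them, every other between-group endpoint is at 6 months, and section 5.2 calls the study exploratory.

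Much of this stands, and it rules out three stronger readings that a reader might infer:

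- **That follow-up ends 6 weeks after the last injection.** Sections 6.2, 6.3 and 6.5 say otherwise, and 6.1 refers to the last administration of study treatment, which may include traction.
- **That the planned arm comparison is invalid after crossover.** No section states a 12-month between-arm comparison of adverse events, and crossover does not affect the 6-month comparison. The defect is that 5.2 does not exclude the later one.
- **That controls cannot have recorded events before crossover, so their count is zero by construction.** Section 6.1 sets an end point, not a start, and the questioning in 6.5 makes no exception for untreated men.

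The reply does not remove the conflict. The section titled as the reporting period states a limit for new symptoms that 6.5 does not share. Section 6.3 depends on a belief that the event is related, formed by men who know whether they were treated, and 6.2 is confined to clinically significant findings. No section says which rule prevails.

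**Conclusion.** The point holds as a conflict between 6.1 on one side and 6.5 and 2.2 item 7 on the other, together with an unbounded comparison in 5.2. If 6.1 is followed, new non-serious events over about 26 weeks (about 20 if traction is study treatment) in about three quarters of men may be missing from the 12-month report. How many would be lost cannot be estimated: the documents give no event rates, and the other sections would capture some or all of them. The gap in weeks rests on 26 weeks for the 6-month phase and on reading 6.1 alone; the shares of follow-up also rest on the assumed 4- to 8-week spacing. A cumulative or 12-month cohort comparison, if made, could not be read as treated against untreated. The curvature and PDQ primary endpoints are not affected.

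**What to change.** - **Sections 6.1, 6.5 and 2.2:** reconcile them to one recording period in both arms, from randomisation to the last study visit. If the 6-week period is kept for another purpose, such as classifying events as on-treatment, say so, and say whether traction counts as study treatment.
- **Section 6.5 and the schedule in 3.5:** ask the same adverse event questions in both arms at the end of the randomised phase. The 3.5 table has no adverse event row, and CCH men have assessments at each series that untreated controls do not.
- **Section 5.2:** limit the between-arm comparison to the randomised period before crossover, over the same length of time in each arm. On the assumed spacing, the CCH arm's 6-week visit falls at week 18 to 30, against week 26 for the controls' assessment.
- **Later events:** report them descriptively by exposure period (CCH-first men after treatment; controls during and after crossover CCH).

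The cost is a wording change, a few more recorded events and one more safety table. Sample size and visits stay the same.
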